6.2 Data Analysis

6.2.1 Planned recruitment rate

The project has a total duration of 63 months: set-up (6 months); internal pilot (9 months); recruitment (39 months); final follow-up (6-months) and analysis, reporting and dissemination (3 months).

Recruitment has been modelled on ongoing critical care studies (e.g. MARCH [30] and ADAPT-sepsis [32] trials).

Critical care studies typically target recruitment at 1-2 patients/ site/ month. Currently, in the ongoing MARCH trial (commenced recruitment post-pandemic), recruitment (up to April 2023) is at a rate of 1.1-1.2 patients/site/month.

Based on staggered site set-up, we will need a total of 32 sites for the pilot and 44 sites for the main trial. Our recruitment and site set-up projections are shown in Figure 2.

We are cognisant of the challenges of delivering care trials. To optimise recruitment, we will engage closely with medical and nursing research networks across anaesthesia, respiratory medicine, emergency medicine and critical care. This engagement will also help develop research capacity for the future. We also anticipate developing a network of local and regional trial champions to ensure ongoing site engagement and discussion.

[figure not shown]

Figure 3 PROTECT Airways Site and Recruitment Projection Chart

6.2.2 Statistical analysis plan

Primary outcome analyses

The outcome summaries and analyses will adopt the Estimand framework (as cited by the ICH E9 (R1) addendum on Estimand and sensitivity analyses in clinical trials) [33].

Summary measure and the primary Estimand: The duration of mechanical ventilation (in days) will be summarised using median, interquartile range, mean and standard deviation. The statistical analysis for this outcome will be done using the treatment policy strategy (i.e. intention to treat). Time-to event (survival models) analysis will be used to estimate the treatment effect by summarising hazards odds ratios (and 95% confidence intervals), using both unadjusted and adjusted (for site and adjusting for e.g. age and illness severity (APACHE II)) estimates. Kaplan-Meier plots will be used to display the duration of ventilation accommodating for the censored values. Intercurrent events (ICEs) and strategies for handling ICEs: post-randomisation events that may affect the interpretation of the primary outcome will include: (a) death (ICE 1); (b) cross-over (ICE 2); (b) non-compliance (including discontinuation of treatment) (ICE 3). The ICE 1 will be analysed using a composite strategy and applying competing risk models. Fine and Gray competing risk regression will be used to assess duration of ventilation, in the presence of death[34]. Competing risk regression models address the situation when more than one mutually exclusive endpoint is possible: in this case, successful extubation or death. This analysis provides a sub-distribution hazard ratio (SHR), the magnitude of which is affected by both the time to coming off the ventilator and the probability of death. SHR assesses the association between an intervention and extubation, accounting for the existence of the alternative outcome of death. The ICE 2 and ICE 3 will be analysed using the principal stratum strategy. For the ICE 2, we will

use the inverse probability weighted analysis method to assess the treatment effect, having taken account of these events [35]. We will also assess the impact of crossovers on the statistical power of the study: due to the contamination effect in patients who crossover from one intervention to another, there is likely to be a reduction in the trial power. We will examine the loss of power, using power curves and different degrees of crossover, pivoted around the observed crossover rates, and assess this at the end of the pilot study as well as presenting these to the DMC at each 6-monthly analysis [36]. For ICE 3, we will use compliers average causal effect (CACE) analyses [37].

Secondary outcome analysis

In general, continuous baseline and outcome data will be summarised with descriptive statistics, including n, mean, standard deviation, median, interquartile range, and n of missing data. Mixed-effects linear regression models will be used to estimate mean treatment differences (95% CI). Categorical baseline and outcome data will be summarised with frequency counts and percentages and mixed-effects logistic regression models will be used to estimate the difference in binary outcomes between treatment groups, with odds ratios and 95% CIs reported.

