6. STATISTICAL ANALYSIS

6.1 Power and sample size

We will recruit 2194 patients (1097 per arm) in total (using 90% power, 5% alpha level). Using methods based on survival analysis, the following parameters have been used for the estimation of the sample size:

- *Duration of invasive mechanical ventilation (control arm)*. Based on 133,291 admissions to 209 adult, general critical care units 1 April 2011 – 31 March 2012, the median duration of mechanical ventilation, for this trial was taken as 6 days [29].
- *Minimal clinically important difference*: In the ongoing NIHR HTA MARCH trial [30] and the BREATHE study [25], a clinically important difference of 1 day was considered to be meaningful (as defined by clinical ICU-based investigators and patient and public representatives).
- *Loss-to-follow-up*: Using the ICNARC Quarterly Quality Report Manchester Royal Infirmary, Intensive Care/High Dependency Unit (1 April 2018 to 31 March 2019) based on 2,535 patients the mortality of ventilated patients averaged at 25.6% (ICNARC, Case Mix Programme Report, 2019- obtained from ICNARC). Thus, the sample size has been inflated, to account for this loss to follow-up.
- *Withdrawal rate*: We anticipate a low rate of withdrawal of patients, as the primary outcome will be measured during the hospital stay. In our previous trials, we have consistency observed low rates of withdrawals (e.g. RECOVERY-RS 1% [24] ; BREATHE 0% [25]; HARP-2 0.5% [26]; REST 1.7% [27]). For this trial we have very conservatively assumed a withdrawal rate of 3%.
- From the above, we derive a hazard ratio of 1.2 (i.e., 6/5 days). It is anticipated that the hazards may not be constant over time (as assumed for the exponential distribution) and that the hazards are quite likely to decrease over time (as observed in the BREATHE study [31]). For this reason, the Weibull distribution may be more of an appropriate distribution, as it computes a shape parameter, p , which allows for non-constant hazards. Using the data from the BREATHE study [31], we derived the shape parameter, p , as 0.901. The hazard ratio is adjusted for this parameter and the sample size computed using the survival analysis methods.

We will review the sample size parameters with the DMC at the end of the pilot stage, using the observed data.

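### Section 6.2.2 gives the primary outcome conflicting intercurrent-event strategies and does not say whether the hazard ratio or the Fine-Gray ratio carries the 5% test

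*Protocol*

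**What the plan says.** Section 6.2.2 of the protocol opens its primary-outcome text with a label for the summary measure and primary estimand. Under it stands: "The statistical analysis for this outcome will be done using the treatment policy strategy (i.e. intention to treat"). Time-to-event models follow, giving unadjusted and adjusted estimates (site, and for example age and APACHE II), with Kaplan-Meier plots that allow for censoring.

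The same paragraph then lists three intercurrent events for this outcome:

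- **Death:** "The ICE 1 will be analysed using a composite strategy and applying competing risk models". The model is Fine and Gray and the measure is the SHR.
- **Crossover and non-compliance:** "The ICE 2 and ICE 3 will be analysed using the principal stratum strategy". Crossover is handled by inverse probability weighting (IPW) and non-compliance by a complier average causal effect (CACE).

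Section 6.1 gives one error level for the whole trial: "We will recruit 2194 patients (1097 per arm) in total (using 90% power, 5% alpha level").

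**The concern.** Two things in the paragraph do not fit together.

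First, crossover and non-compliance carry two strategies. Treatment policy keeps everyone as randomised and ignores whether these events occurred. Principal stratum asks about the effect in a subset defined by compliance. One estimand cannot use both for the same events, and the paragraph does not mark either as secondary.

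Second, death can be handled in two ways within an all-randomised analysis, and the paragraph appears to plan both. A hazard ratio that censors deaths compares the rate of liberation among patients still alive and ventilated. The SHR keeps patients who died in the risk set as never liberated, so it moves with mortality as well as with speed of liberation. If the two differ, the reader cannot tell which one is the trial's answer, or which one the stated 90% power belongs to.

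**Working it through.** **Inputs from section 6.1.** 2194 patients, 1:1; control median 6 days; hazard ratio 1.2; Weibull shape 0.901; mortality 25.6%, counted as loss to follow-up; withdrawal 3%; 90% power; 5% alpha with sidedness not stated.

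**Step 1: which test does 2194 belong to?**

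- Shape-adjusted hazard ratio: 1.2^0.901 = 1.1785, and ln(1.1785) = 0.1643.
- Two-sided 5%, 90% power: (1.960 + 1.282)² = 10.51.
- Schoenfeld events: 4 × 10.51 / 0.1643² = 1558.
- Freedman events: 10.51 × (2.1785/0.1785)² = 1565.
- Deaths and withdrawals removed as losses: 1558/(1 − 0.256 − 0.03) = 2182 and 1565/0.714 = 2192. Dividing by 0.744 × 0.97 instead gives 2159 and 2169.

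All four are within 3% of 2194. One-sided 5% gives at most 1787, and an unadjusted hazard ratio of 1.2 gives at most 1782. The plan's figure is therefore reproduced by one two-sided 5% test of a hazard ratio with deaths treated as losses.

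**Step 2: what the same effect looks like as an SHR.** Assume proportional cause-specific hazards, with 25.6% of controls dying on the ventilator and no effect on death. Eventual liberation is then 74.4% in controls and 0.744 × 1.1785 / (0.744 × 1.1785 + 0.256) = 77.4% with the device. The ratio of cumulative sub-distribution hazards starts near 1.18 and falls to ln(1 − 0.774)/ln(1 − 0.744) = 1.09 by the end of follow-up. The SHR is an average over that path, so it is weaker than 1.18.

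**Step 3: simulation.** 2194 patients, 6-day median time to liberation or death, 25.6% of controls dying on the ventilator, no covariates, no withdrawal. Two unadjusted tests are compared: log-rank censoring deaths, and the Fine-Gray equivalent with deaths kept at risk. Shapes 1 and 0.901 give the same results, because these are rank tests. The ranges cover several independent runs.

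| Scenario | HR, deaths censored | SHR | Tests disagree on p<0.05 |
|---|---|---|---|
| Liberation HR 1.1785, no effect on death | about 92% significant | about 68% | about 25-26% |
| No effect on liberation, death HR 0.8 or 1.25 | about 5% | about 38-42% | about 38-43% |

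Adding 3% withdrawal gives 91% and 67% in the first row. With assumed prognostic covariates, disagreement under the design effect ranges up to 29%.

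**Step 4: false positives, only if any significant result counted.** The correlation of the two statistics under the null is about 0.73.

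- HR or SHR, unadjusted: 7.7-8.7% across runs and covariate assumptions.
- Unadjusted and adjusted versions of both: 8.4-10.9%, depending on assumed covariate strength.
- IPW counted as well: 9.5-12.3%, with assumed crossover of 3-5% and non-compliance of 10-20%.
- CACE was taken as the same test as intention to treat under the null, so it adds essentially nothing.
- SHR and IPW only: 6.3-6.9%.
- One named analysis: 5%.

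**The case against.** The strongest reply is that the protocol does name a primary strategy. Treatment policy sits directly under the primary-estimand label. Section 2.10, on crossover and non-compliance, says the impact of these events will also be assessed through the estimand framework, which reads as additional work. On that reading intention to treat decides, and IPW and CACE are supplementary. This largely stands. It does not remove the principal-stratum sentence, which section 6.2.2 leaves unqualified.

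A second reply is that censoring of deaths is inferred. The censored values in the Kaplan-Meier sentence could be withdrawals, and intention to treat with Fine-Gray for death would be one coherent contrast. That reading is possible. Against it, section 6.1 counts deaths as loss to follow-up, and its sample size is reproduced only that way. Section 6.4 assumes no censoring at all, so the protocol is not consistent on this point.

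A third reply is that hierarchy and adjustment are usually settled in the analysis plan, which section 2.10 promises before recruitment ends. For missing detail that would be enough. Here the statements conflict, in an open-label trial with an unblinded statistician.

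A reader might infer that no analysis is named as deciding, that each is tested at a full 5%, and that the trial therefore has a false-positive rate of about 8-11%. The document does not support this. Intention to treat is named, alpha appears once, and no rule lets any significant result count as success. Nor does the principal-stratum conflict drive that figure, which comes mostly from hazard ratio versus SHR and from adjustment.

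**Conclusion.** The point holds as a contradiction in the text and an open choice with consequences. Crossover and non-compliance carry two incompatible strategies, although intention to treat is the natural primary. The measure that handles death is undecided, and so is unadjusted versus adjusted.

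The size that matters is the power gap of about 92% against 68%, with disagreement in about 26% of trials under the design effect. Neither figure needs any rule about claiming success. Both rest on proportional cause-specific hazards, on all of the 25.6% mortality occurring before liberation, and on no device effect on death. If the device also lowers mortality the SHR gains: at a death hazard ratio of 0.85 its simulated power was 94%. The false-positive rate of about 8%, or roughly 8-12% with adjusted and weighted versions, is conditional on a rule the protocol does not contain. It is not a property of the plan.

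**What to change.** In section 6.2.2:

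1. State that the deciding analysis includes all randomised patients, with treatment policy for crossover and non-compliance.
2. Replace the principal-stratum sentence with wording that makes the IPW and CACE analyses supplementary estimands.
3. Name one effect measure for death (hazard ratio or SHR) and one adjustment set as deciding at two-sided 5%. Label the other estimates supportive and unable to change the trial's conclusion.

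In section 6.1, state that the 5% is two-sided and which measure it applies to. If the SHR is chosen, restate the design effect and power on the SHR scale, because the stated 90% is reproduced only for the hazard ratio with deaths treated as losses.

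The wording needs no new data. The sponsor gives up choosing among the analyses after the results are seen. If the SHR decides, the stated power may become less favourable, and the sample size may need review.

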2.3 Aims and objectives

Objectives:

- (1) Conduct an internal pilot study to confirm the feasibility of a large-scale multicentre trial.
- (2) To conduct a UK-wide multi-centre, open-label, pragmatic, individually randomised, parallel group trial and economic evaluation to determine the clinical and cost effectiveness of an advanced airways protection device versus conventional endotracheal tubes (with and without basic subglottic manual suction and standard cuff) in patients with respiratory failure requiring mechanical ventilation. The outcomes are duration of mechanical ventilation, survival, ICU, and hospital stay outcomes and health-related quality of life.
- (3) Estimate, in an integrated economic evaluation, the cost-effectiveness of an advanced airways protection device versus the conventional endotracheal tubes.

Justification of outcomes

We have worked with patients, the public, researchers and clinicians to determine both our primary and secondary outcomes. This clinical effectiveness trial comprises key core outcomes from the Core Outcomes in Ventilation Trials (COVent) core outcome set and NICE guidelines for ventilation trials and NICE guidelines [5, 12, 13].

Primary effectiveness outcome

The primary variable (outcome) of interest is the duration of mechanical ventilation as measured from time from randomisation to first successful unassisted breathing, measured in days. This outcome is one of the 'COVenT' core outcomes for trials of interventions intended to modify the duration of mechanical ventilation[14]. To clarify:

- Unassisted breathing is defined as no inspiratory support or extracorporeal lung support
- Success is defined as maintaining unassisted breathing at 48 hours.
- Duration includes time receiving extracorporeal lung support, invasive mechanical ventilation and non-invasive ventilation delivering volume or pressure support ventilation.
- Duration excludes time receiving high-flow oxygen therapy and continuous positive airway pressure.
- Patients with a tracheostomy in situ may still achieve successful unassisted breathing.

Secondary outcomes - refer to CoReCCT master protocol for core clinical outcome set.

Effectiveness

- *Duration of endotracheal intubation*: time from randomisation to endotracheal extubation (in hours).
- Ventilator Associated Pneumonia (VAP): Diagnosed by treating clinician with commencement of antibiotics [16] from randomisation up to ICU discharge.

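### Section 6.2.2 names extubation as the event in the competing-risk model for the primary outcome, while section 2.3 defines that event as successful unassisted breathing

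*Protocol*

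**What the plan says.** Protocol section 2.3 sets the primary outcome as "duration of mechanical ventilation as measured from time from randomisation to first successful unassisted breathing, measured in days" and adds clarifications:

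- Breathing counts as unassisted when the patient has neither inspiratory nor extracorporeal support, and as successful when this still holds at 48 hours.
- On what counts towards the total: "Duration includes time receiving extracorporeal lung support, invasive mechanical ventilation and non-invasive ventilation delivering volume or pressure support ventilation".
- On patients who have had a tracheostomy: "Patients with a tracheostomy in situ may still achieve successful unassisted breathing".

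The same section lists the time from randomisation to endotracheal extubation, in hours, as a secondary outcome of its own.

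Protocol section 6.2.2, under the primary outcome analyses, introduces Fine and Gray regression as the strategy for death (intercurrent event 1). It states the model's endpoints as follows: "Competing risk regression models address the situation when more than one mutually exclusive endpoint is possible: in this case, successful extubation or death". It then interprets the estimate: "SHR assesses the association between an intervention and extubation, accounting for the existence of the alternative outcome of death". Between these points the paragraph also says that the model is there to assess how long ventilation lasts, and that the SHR depends on when patients come off the ventilator. Earlier in the section there is a separate time-to-event analysis of ventilation duration under a treatment-policy strategy, with Kaplan-Meier plots. That text does not use extubation as the event.

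**The concern.** A time-to-event model is defined by its event. Here the protocol gives two events for one primary-outcome model, and its own outcome list treats them as different endpoints. The 48-hour success rule in section 2.3 is attached to unassisted breathing, and this protocol does not define a successful extubation.

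The two events part company in patients who fall within the trial's scope. Section 2.4.2 excludes a tracheostomy only at screening, and section 2.7 says that later tracheostomy is regarded as an important outcome. Section 2.9 leaves non-invasive respiratory strategies to the clinical team. A model fitted with extubation as its event would estimate an effect on tube removal, which section 2.3 makes secondary, and would report it under the primary outcome. Section 6.1 puts mortality among ventilated patients at 25.6%, so the analysis that deals with death is not a side issue.

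**Working it through.** **Step 1: does the sample size depend on the point?** Inputs from section 6.1: hazard ratio 1.2, Weibull shape 0.901, 90% power, 5% alpha (taken as two-sided, since sidedness is not stated), 25.6% mortality and 3% withdrawal.

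- Adjusted hazard ratio: 1.2^0.901 = 1.1785.
- Freedman events: (1.960 + 1.282)² × ((1 + 1.1785)/(1 − 1.1785))² ≈ 1565, or 783 per arm after rounding up.
- Inflation: 783/(1 − 0.256 − 0.03) = 783/0.714 = 1096.6, rounded up to 1097 per arm, or 2194 in total.

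This is the protocol's figure. Its inputs are stated for duration of mechanical ventilation, and aligning the event wording changes none of them.

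**Step 2: compare the two events by patient course.**

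| Course | Event time under section 2.3 | Event time under section 6.2.2 as worded |
|---|---|---|
| Extubated with no further inspiratory or extracorporeal support, still so at 48 hours | Extubation | Extubation (agrees) |
| Extubated to high-flow oxygen or continuous positive airway pressure, which section 2.3 leaves out of the duration | Extubation | Extubation (agrees) |
| Extubated to NIV with pressure or volume support | End of that support, if maintained at 48 hours | Extubation (too early) |
| Oral tube replaced by a tracheostomy, still ventilated | When ventilator support stops, if maintained at 48 hours | Removal of the oral tube (too early), or no clear event |

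An invented case for the last row: tracheostomy on day 10 and free of support on day 20, counted from randomisation. Section 2.3 gives 20 days. Taking removal of the oral tube as the event gives 10.

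**Step 3: can the effect be sized?** Not from the protocol, which gives no rate of tracheostomy or of NIV after extubation. An illustration on assumptions only: Weibull times with shape 0.901 and medians of 6 and 5 days; 5–20% of patients with a tracheostomy, their oral tube out at half the time to liberation; and 5–10% extubated to NIV at 80% of that time. Deaths are left out. Simulated medians using extubation as the event:

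| Tracheostomy, NIV | Control | Intervention | Difference | Ratio |
|---|---|---|---|---|
| 5%, 5% | 5.71 | 4.78 | 0.93 | 1.19 |
| 10%, 10% | 5.45 | 4.54 | 0.91 | 1.20 |
| 20%, 10% | 5.05 | 4.23 | 0.82 | 1.19 |

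The control median falls from 6.0 to about 5.7–5.0 days, and the difference from 1.0 to about 0.9–0.8 day. The ratio stays near 1.2 by construction, because the same shares and the same proportional shortening were applied to both arms. The illustration shows the direction of the shift and does not estimate a bias in the treatment effect.

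**The case against.** The best defence is that extubation is loose shorthand here. The sentence that assigns the Fine and Gray model to an outcome speaks of ventilation duration, which section 2.3 defines in detail, and the paragraph also refers to coming off the ventilator. Both extubation phrases stand in sentences that explain what competing-risk regression does. The trial summary and sections 1.2, 2.10 and 4.1 all keep ventilation duration as the primary outcome. Event coding is normally fixed in the statistical analysis plan, which section 2.10 promises before recruitment ends.

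Much of this stands. A drafting slip is plausible, and any harm depends on the wording being followed. The conflict remains, because the one sentence that lists the model's mutually exclusive endpoints names extubation and the sentence interpreting the SHR repeats it. This is a rule that the protocol states, and states inconsistently, so it is not a detail left for the analysis plan.

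A reader might go further and infer three things that the documents do not support:

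- **That the trial's main result will rest on wrong event times.** Section 6.2.2 also has the treatment-policy analysis without extubation wording, and it does not say which estimate is the headline.
- **That several hundred of the 2194 patients are affected.** Any such count needs tracheostomy and NIV rates that the protocol does not give.
- **That an extubation event is more open to performance bias.** Stopping pressure support is also an unblinded clinical decision, and section 2.10 plans to collect data on readiness to extubate and on reasons for departing from plan.

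**Conclusion.** The point holds as an internal contradiction about the event in one primary-outcome analysis. Section 6.2.2 twice uses extubation where section 2.3 requires successful unassisted breathing, although the same paragraph describes the model as one of ventilation duration. If the wording is followed, event times are too early for patients extubated to pressure- or volume-support NIV, and early or undefined for patients given a tracheostomy. The affected model is the one that accounts for death.

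The size of the effect cannot be derived from the protocol. The shifts in the medians shown above rest wholly on assumed shares and timings. A shift that is equal and proportional in both arms would leave the ratio unchanged, and whether the arms would differ is unknown. The planned sample size is reproduced exactly and does not change.

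**What to change.** In section 6.2.2, replace both mentions of extubation (the endpoint pair and the interpretation of the SHR) with *first successful unassisted breathing as defined in section 2.3*. State that death before that event is the competing event. Keep endotracheal extubation as the event only for the secondary outcome on duration of intubation, and carry the same definition into the statistical analysis plan before it is finalised.

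The cost is two changes of wording and one added clause. Section 2.10 says that ventilation status is already recorded hourly in clinical records, so no new data are needed, and the sample size stays at 2194.
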